## 16 SAFETY EVALUATION AND REPORTING

Deviations from SOPs or the CIP as well as adverse device effects, device deficiencies and adverse events occurring in the context of the investigation are documented. The definitions and reporting requirements adopted in this investigation are derived from the international standard on clinical investigations ISO 14155:2020, the Medical Device Regulation 2017/745 (MDR), MEDDEV 2.7/3. and MDCG 2020-10/1.

### 16.1 Definitions

|                             |   |
|-----------------------------|---|
| Adverse Event (AE)          | 
Any untoward medical occurrence, unintended disease or injury, or any untoward clinical signs (including abnormal laboratory findings) in the context of a clinical investigation in a subject, user, or other person. For users or other persons, this definition is restricted to events related to the use of investigational medical devices or comparators.
 
An adverse device effect (ADE) is a subtype of adverse events. These are adverse events related to the use of an investigational medical device or the comparator (if it is a medical device) and include:
 
 
1. any adverse event resulting from insufficient or inadequate instructions for use, deployment, implantation, installation or operation, or any malfunction of the investigational medical device.
 
2. any event resulting from use error or intentional misuse of the investigational medical device.
 
   |
| Serious Adverse Event (SAE) | 
Any adverse event that led to:
 
 
• death
 
• serious deterioration in health of the subject, user, or other person: 
 
1. a life-threatening illness or injury
 
2. a permanent impairment of a body structure or function, including chronic diseases
 
3. in-patient or prolonged hospitalization
 
4. medical or surgical intervention to prevent life threatening illness, injury or permanent impairment to a body structure or function
 
 
 
• fetal distress, fetal death, a congenital abnormality, or birth defect.
 
 
Planned hospitalization for pre-existing condition, or a procedure required by the CIP, without a serious deterioration in health, is not a serious adverse event.
 
A serious adverse device effect (SADE) is a subtype of serious adverse events. These are serious adverse events related to the use of an investigational medical device or the comparator (if it is a medical device).
 |
| Device deficiency           | 
Any inadequacy of the investigational device or the comparator in the identity, quality, durability, reliability, usability, safety, or performance. This includes malfunctions, use errors and inadequate supply of information.
  |

### 16.2 Recording and reporting of adverse events

The following events are registered (MDR 80:1):

- any adverse event of a type identified in the clinical investigation plan as being critical to the evaluation of the results of that clinical investigation
- any serious adverse event

- any device deficiency that might have led to a serious adverse event if appropriate action had not been taken, intervention had not occurred, or circumstances had been less fortunate
- any new findings in relation to the above events

The events will be registered by the clinic within the adverse events module in the eCRF in a timely manner.

All AEs will be characterized by the following criteria:

- Date of incident
- Intensity or Severity
- Relationship to the investigational device and the related procedure
- Outcome
- Treatment or Action Taken

The investigator shall report events **immediately, but not later than 3 calendar days** after investigational site study personnel's awareness of the event. Any serious adverse events during treatment will be reported as required by national regulations to the relevant authorities. The sponsor is responsible for reviewing all adverse events and ensuring they, if necessary, are reported to the EC and regulatory authorities. The patients involved should be informed as soon as possible. Furthermore, they should be offered counselling and/or support.

If unforeseen technical issues occur, regardless of group affiliation, embryos for transfer will be selected based on morphological assessment only.

### 16.3 Reporting adverse events to all National Competent Authorities

The following are reported by the sponsor:

- any **serious adverse event (SAE)** having a causal or reasonably possible causal relationship with the
  - a) investigational device
  - b) comparator
  - c) investigation procedure
- any **Device Deficiency that might have led to a SAE** if:
  - a) appropriate action had not been taken or
  - b) intervention had not been made or
  - c) if circumstances had been less fortunate
- **new findings/updates** in already reported events.

All reportable events regarding an imminent risk of death, serious injury, or serious illness and that requires prompt remedial action for other patients/subjects, users or other persons are reported **immediately, but not later than 2 calendar days** after awareness by the sponsor. The same deadline applies for updates/new findings regarding this type of events.

Any SAEs reported via the eCRF will also be handled under the post-market surveillance/vigilance system.

Any other reportable events are reported **immediately, but not later than 7 calendar days** after awareness by the sponsor. The same deadline applies for updates/new findings regarding this type of events.

## 16.4 Causality assessment

The relationship between the use of the medical device and the occurrence of each adverse event shall be assessed and categorized. During causality assessment, clinical judgement shall be used and relevant documents (the Investigator's Brochure, the Clinical Investigation Plan or the Risk Analysis Report) shall be consulted. The presence of confounding factors, such as concomitant medication/treatment, the natural history of the underlying disease, other concurrent illness or risk factors shall also be considered. These considerations apply to all serious adverse events, regardless of whether the subject of the event belongs to the control or the investigational group.

Serious adverse events related to the investigational device will be distinguished from those related to the procedures (any procedure specific to the clinical investigation). An adverse event can be related both to procedures and the investigational device. Complications of procedures are considered not related if the procedures would have been applied to the patients also in the absence of investigational device use/application.

Each SAE will be classified according to five levels of causality. The following definitions are used:

| Classification of causality   | A relationship between the SAE and the investigational device or procedures...  |
|-------------------------------|---|
| Not related                   | can be excluded   |
| Unlikely                      | seems not relevant and/or the event can be reasonably explained by another cause  |
| Possible                      | is weak but cannot be ruled out completely.
Cases where relatedness cannot be assessed, or no information has been obtained should also be classified as possible. |
| Probable                      | seems relevant and/or the event cannot reasonably be explained by another cause.  |
| Causal relationship confirmed | is beyond reasonable doubt.   |

## 16.5 Examples of adverse events

Adverse events (AEs) can occur within any clinical or laboratory process (oocyte pick-up, insemination, handling, embryo transfer, cryopreservation) and for instance be caused by the human factor, absence/failure of witnessing or poor-quality systems. The consequences may include reduced/no chance of pregnancy, transmission of disease, psychological impact, and ethical/legal issues. Causal factors must always be investigated.

Examples of relevant SAEs:

- Severe OHSS requiring hospitalization
- Bleeding and/or infection in relation to the oocyte pick-up

Examples of adverse events with a possible impact on the outcome of the investigation

- embryos transferred to the wrong patient
- loss of gametes/embryos resulting in total/decreased loss of chance of pregnancy in one cycle, such as
  - technical failure of incubator or cryotank

- accident with culture dishes,
- embryos discarded by mistake
- embryos lost due to microbial contamination
- labelling error of tubes/dishes containing the oocytes/sperm/embryos
- mix-up of sperm samples during preparation/treatment
- sperm sample contaminated by another sample (e.g. with a used pipette)
- oocytes fertilised with spermatozoa from the wrong person

#### Examples of device deficiencies

- No score due to low-quality images or air bubbles
- Cannot access the software for unknown reasons

### 16.6 Summary of registering and reporting events

| Type of event                    | Registered  | Reported  |
|----------------------------------|---|---|
| Adverse event                    | Yes, if it has been identified in the CIP as being critical to the evaluation of the results of the clinical investigation.                           | No  |
| Serious adverse event            | Yes   | Yes, if a causal relationship with the investigational device, the comparator or the investigation procedure exists or is reasonably possible.        |
| Device deficiency                | Yes, if it might have led to a SAE if appropriate action had not been taken, intervention had not occurred, or circumstances had been less fortunate. | Yes, if it might have led to a SAE if appropriate action had not been taken, intervention had not occurred, or circumstances had been less fortunate. |
| New findings of any of the above | Yes   | Yes, if reported, otherwise no.   |
|                                  |   |   |

## 17 PUBLICATION POLICY

The clinical investigation is registered in a publicly accessible database ([see the synopsis table](#)). The results of the investigation will be made publicly available and offered for publication in scientific journals regardless of the outcome.

The personal data of participants will remain confidential. Study reports will not contain any information that can identify participants. However, the sponsor's monitor or representative and regulatory representatives, auditors and inspectors may need access to medical records to verify the authenticity of collected data.

### 17.1 Main results

- The primary results of this RCT will be announced in one of the major conferences in the field of Reproductive Medicine.
- The main publication reporting the results of the primary outcome (first phase of the trial) will be submitted for publication in a journal of high impact factor.

To evaluate the contribution that any effect makes to clinical care by:

Measuring the number of cycles where iDAScore affects the decision about which embryo is to be transferred in the first embryo transfer.

### 17.2 Ethical oversight

The study will be overseen by the relevant institutional ethics committee. Ethical approval for the study has been obtained for an earlier version of this study protocol (version 20) of this protocol from several Ethics committees. Further approval for this version will be sought.

# APPENDIX 1. SCORING OF DAY 5-6 EMBRYOS

## This procedure details:

- The Blastocyst Stage Grading that is to occur in all Laboratories.
- This process cannot be duplicated/paraphrased or copied into state quality system documents.
- The state laboratory policies/work instructions must refer back to this document whenever Cleavage Stage Grading occurs.

## Responsibility:

- Documents has been prepared by agreement between all Scientific Directors, and can only be changed by agreement of these Scientific Directors

## Expected Development stages of Embryos-Blastocysts:

- Day 2 Embryos: 2 to 6 cells.
- Day 3 Embryos:  $\geq 6$  cells. May also be compacting (early morula).
- Day 4 Embryos: early morula (compacting) or morula. It is also not unusual to see 10 and 12 cell embryos at this stage, or very early blastocysts (cavitating morula).
- Day 5 Embryos: morula, early blastocyst, blastocyst, expanded blastocyst, hatching blastocyst, or hatched blastocyst.

### Blastocyst stage grading:

1. Blastocyst stage grading is based on a 3-stage system incorporating the degree of expansion, Trophectoderm status, and Inner Cell Mass status.
2. On D5 and D6, there is an increasing Pregnancy rate as the Gardner scale increases (0-to-6).
3. The recommendation is that D5 and D6 blastocysts with any combination of ICM or Trophectoderm quality grading of "C", will not be transferred or cryopreserved, except under the specific direction of the managing physician:

| As defined on D5 (114-118hpi), or D6 (138-142hpi) |                     |  |
|---|---------------------|--|
| Exp. Grade  | Development Stage   | Definition   |
| 0   | Cleavage Stage      | Still at Cleavage stage. Blastomeres visible.  |
| C   | Compacting          | Cell membranes/borders becoming undefined.   |
| M   | Morula              | Full compaction, blastomeres not clearly visible. No cavitation visible.   |
| 1   | Cavitating          | Blastocoel takes up less than half the space of the embryo.  |
| 2   | Early Blastocyst    | Blastocoel takes up greater than, or equal to half the space of the embryo.  |
| 3   | Blastocyst          | Blastocoel expanded into the entire volume of the embryo, pressing the Trophectoderm cells tightly against the inside of the zona pellucida. |
| 4   | Expanded blastocyst | Blastocoel volume larger than that of the early embryo, zona pellucida is thinning.  |
| 5   | Hatching Blastocyst | Blastocyst is beginning to herniate out of the zona pellucida.   |
| 6   | Hatched Blastocyst  | Blastocyst has completely hatched out of the zona pellucida.   |
| D   | Degenerate          | Majority of cells show signs of necrosis, apoptosis.   |
| P   | Pulsing / Collapsed | Blastocyst which had been expanded, but upon assessment has collapsed, or 'pulsed' so that the cells are pulled away from the zona.          |

| Inner Cell Mass Grading (Blasts at stage 3,4,5,6) |         |                                |
|---|---------|--------------------------------|
| Gardner ICM                                       | Quality | Definition                     |
| A   | Good    | Many cells, tightly packed     |
| B   | Fair    | Several cells, loosely grouped |
| C   | Poor    | Very few cells                 |

| Trophectoderm Grading (Blasts at stage 3,4,5,6) |         |  |
|---|---------|--|
| Gardner Trophectoderm                           | Quality | Definition                               |
| A   | Good    | Many cells forming a cohesive epithelium |
| B   | Fair    | Continuous but irregular cells           |
| C   | Poor    | Patchy epithelium with few cells         |

Ranking guideline for Group A (standard morphologic criteria) for Day 5 fresh embryo transfers:

| Ranking guidelines |   |
|--------------------|---|
| Order              | 
 
1. Developmental stage 6 > 5 > 4 > 3
 
2. TE grade A > B
 
3. ICM grade A > B
 
4. Developmental stage 2 > 1
 
5. Any combination of ICM or Trophectoderm quality grading of "C", or embryos with developmental stage graded as "Morula" or below, will not be transferred or cryopreserved, except under the specific direction of the managing physician.
 
 |
| Examples           | 
A blastocyst graded as '5BB' will be chosen over '4AA'
 
A blastocyst graded as '4BA' will be chosen over '4AB'
 
A blastocyst graded as '2' will be chosen over '4BC'
   |

Ranking guideline for Group A (standard morphologic criteria) for frozen embryo transfers:

| Ranking guidelines |   |
|--------------------|---|
| Principles         | 
The warming of embryos will proceed on the ranking guidelines across embryos vitrified on Day 5 or 6
 
The first embryo to be warmed will be the one with the highest morphological grading, followed by day of vitrification
   |
| Order              | 
 
1. Developmental stage 6 > 5 > 4 > 3
 
2. TE grade A > B
 
3. ICM grade A > B
 
4. Day 5 > Day 6
 
5. If vitrified, any blastocyst combination of ICM or Trophectoderm quality grading of "C" will be warmed last
 
 |
| Examples           | 
A Day 6 blastocyst graded as '5AA' will be chosen over a Day 5 '4AA'
 
A Day 5 blastocyst graded as '4AA' will be chosen over a Day 6 '4AA'
 
A Day 6 blastocyst graded as '4BA' will be chosen over Day 5 blastocyst '4AB'
  |

1 STUDY DETAILS

Study Objectives

The **primary objective** for this study is to investigate whether selection of a single blastocyst for transfer using the deep learning-based support tool called iDAScore results in a non-inferior clinical pregnancy rate compared to when the selection is performed by trained embryologists using conventional morphology only. Clinical pregnancy is defined in this study as the detection of a fetal heartbeat (FHB) by ultrasound after 42 days of gestation (week 6) (including ectopic pregnancies, as per the ICMART definition).

The **secondary objectives** for this study are:

To investigate whether blastocyst selection supported by iDAScore results in non-inferior rates of the below parameters compared to when embryo selection performed by trained embryologists using conventional morphology only:

1. Live birth rate* (defined as the number of patients with at least one live birth after 22 completed weeks of gestation. If the exact gestational age is not known then a birth weight of ≥ 500 gr can be used as a cut-off).
2. Positive β -hCG rate (defined as the number of patients with a positive β -hCG, determined by a hCG measurement from a blood sample or using urinary sticks).
3. Rate of non-viable pregnancies (defined as the difference between number of clinical pregnancies (excluding ectopic pregnancies) and number of positive β -hCG pregnancies)
4. Ongoing pregnancy rate* (defined as the number of patients with a viable pregnancy at ≥ 12 weeks of gestation)

*These secondary parameters will not be included in the first statistical analysis and report as these will not be available until approximately 12 months after the initial data collection.

STATISTISKA KONSULTGRUPPEN		Statistical Analysis Plan	
Protocol:		Protocol No: <protocol number>	
eValuating iDA Selection Ability. The VISA study.		Version: 2.0	Page 8 of 25

Study Design

This is a non-inferiority, prospective parallel group, double blind, randomized controlled trial in 15 IVF centres in 4 countries (Australia, Denmark, Sweden and United Kingdom).

Treatment Groups

Patients will be randomly allocated (1:1) to two different study groups if at least two embryos have developed to the blastocysts stage (Gardner score 2 or higher):

A. Control group: Embryo selection by standard morphologic criteria.

- The embryo for transfer will be selected by the embryologist based on the morphologic appearances on day 5, according to the Gardner criteria (Gardner et al., 2000) using the ranking guideline (Appendix 1, in CIP).
- Regardless of whether a transfer takes place any embryos that fulfil the criteria applied in the laboratory for cryopreservation will be cryopreserved (Appendix 1 in the clinical investigation protocol (CIP)). If there is doubt about whether an embryo is suitable for cryopreservation, embryos may be held over to day 6 and the decision will be made then.
- The order of rewarming and transfer of cryopreserved embryos for later transfer will be made according to Appendix 1 in the CIP based on the all the information that is available by day 6.

B. Treatment group: Embryo selection supported by iDAScore.

- The time-lapse videos will be analysed by iDA at 114-118 hours post insemination (hpi) and the embryo with the highest iDA score will be selected for fresh transfer on day 5.
- Any remaining viable embryos in this group will be cryopreserved if they have either:

STATISTISKA KONSULTGRUPPEN		Statistical Analysis Plan	
Protocol:		Protocol No: <protocol number>	
eValuating iDA Selection Ability. The VISA study.		Version: 2.0	Page 9 of 25

- reached Gardner Grade 3 or beyond AND would normally be cryopreserved or;
- have reached Gardner Grade 3 AND achieved a score on iDA of 5 or more.
- All other embryos will be cultured until day 6, re-scored at 138-142 hpi and according to the above criteria.
- The warming and transfer of embryos will be performed based on the ranking of the iDA score across the two days. The first embryo to be warmed will be the one with the highest iDAScore. If this embryo does not survive warming and is not suitable for transfer, the next embryo to be warmed will be selected based on the iDAScore, until an embryo is warmed and is suitable for transfer.

Embryo transfer will be performed using the clinic's routine methods. Luteal support will be administered using the standard protocol of each clinic. Both the treating clinician and the patient will remain blinded to the randomization outcome until after the first embryo transfer has been completed.

Sample Size calculation

It is estimated from the results in clinics that clinical pregnancy is estimated to be 35.4% for trained embryologists. If non-inferiority margin is defined as - 5%, the lower limit of the two-sided 95% confidence interval (CI) for the difference between iDAScore group and Trained embryologist group shall not be less than -5% with a probability of 90% ($\beta=10\%$), with an estimation of 5% or more clinical pregnancies in iDAScore group, 494 women per randomization group is needed to show non- inferiority with two-sided Farrington-Manning test. For protection against a 5% loss to follow-up, 1040 patients in total, 520 per group, are needed for recruitment.

STATISTISKA KONSULTGRUPPEN		Statistical Analysis Plan	
Protocol:		Protocol No: <protocol number>	
eValuating iDA Selection Ability. The VISA study.		Version: 2.0	Page 10 of 25

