### 9.2 Secondary endpoints

- Live birth
- Positive hCG, determined by a hCG measurement from a blood sample or using urinary sticks
- Non-viable intrauterine pregnancy, as witnessed by miscarriage
- Ongoing pregnancy rate in patients with maternal age above 35

See section 10.6 and chapter 14 for more details.

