### 10.6 IVF-Cycle outcome

The outcome of the cycle will be determined by the following assessments:

- Pregnancy will be tested either through a hCG measurement carried out from Day 9-13 following embryo transfer or using urinary sticks (25 IU/L) on day 13.
- A transvaginal ultrasound performed between 28 and 42 days after the embryo transfer (between 7 and 9 weeks of gestation).

Additional hCG measurements and ultrasounds may be performed according to the directions of the supervising physician.

Based on these assessments, the initial outcome of the first embryo transfer cycle will be categorized as:

|  |  |
|--|--|
| Not pregnant                            | Negative test result; urinary hCG < 25 IU/L with urine sticks, hCG in blood < 50 IU/L  |
| Biochemical pregnancy                   | Positive test result with regard to the above cut-off values, but no other clinical evidence of pregnancy, includes pregnancy of unknown location                        |
| Ectopic pregnancy                       | No intrauterine pregnancy and, either ultrasound evidence of a fetal heart outside the uterus or histopathological evidence of ectopic pregnancy excised by laparoscopy. |
| Non-viable intrauterine pregnancy       | Ultrasound evidence of an intrauterine pregnancy but with no fetal heart observed after 7-9 weeks of gestation.  |
| Clinical pregnancy with fetal heartbeat | Ultrasound evidence of an intrauterine pregnancy with a fetal heart observed after 7-9 weeks of gestation.   |

In the case of a clinical pregnancy with fetal heartbeat, the eventual outcome of the pregnancy will be followed and recorded.

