##### **Secondary efficacy variables**

- Live birth rate
- Positive hCG rate per randomized patient
- Rate of non-viable intrauterine pregnancies (as described above)
- Ongoing pregnancy rate in patients with maternal age above 35

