4.1.3 Secondary efficacy Variables

Secondary efficacy variables will be the following outcome variables:

- Live birth (Y/N). Will be analysed in a second database lock.
With pass criteria non-inferiority analysis, non-inferiority margin -5%.

STATISTISKA KONSULTGRUPPEN		Statistical Analysis Plan	
Protocol:		Protocol No: <protocol number>	
eValuating iDA Selection Ability. The VISA study.		Version: 2.0	Page 14 of 25

- Positive hCG rate per randomized patient
With pass criteria non-inferiority analysis, non-inferiority margin -5%.
- Non-viable intrauterine pregnancies

Safety Variables

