5.1.1 Secondary Efficacy Analyses

The secondary efficacy analyses will be the analysis of the secondary efficacy variables defined in section 4.1.3 “Secondary efficacy variables” according to the methods given in section 5, under “General Statistical Methodology”.

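### The SAP's only formula for non-viable pregnancies also counts biochemical and ectopic pregnancies, while the endpoint named in SAP 4.1.3 and the protocol is non-viable intrauterine pregnancy alone

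*SAP*

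**What the plan says.** **SAP section 1, secondary objective 3:** "Rate of non-viable pregnancies (defined as the difference between number of clinical pregnancies (excluding ectopic pregnancies) and number of positive" hCG pregnancies. The same section defines clinical pregnancy as a heartbeat on ultrasound after 42 days of gestation and states that ectopic pregnancies are included. Positive hCG is any positive blood or urine test.

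**SAP 4.1.3** lists the variable only as "Non-viable intrauterine pregnancies", with no derivation. **SAP 5.1.1** says that the secondary analyses are "the analysis of the secondary efficacy variables defined in section 4.1.3".

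**Protocol 9.2** gives "Non-viable intrauterine pregnancy, as witnessed by miscarriage", then adds "See section 10.6 and chapter 14 for more details". **Protocol 14.4** has "Rate of non-viable intrauterine pregnancies (as described above").

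**Protocol 10.6** sorts the first transfer cycle into separate classes. Non-viable intrauterine pregnancy is "Ultrasound evidence of an intrauterine pregnancy but with no fetal heart observed after 7-9 weeks of gestation". Biochemical pregnancy is a positive test with "no other clinical evidence of pregnancy, includes pregnancy of unknown location". Ectopic pregnancy is a third class and includes a fetal heart seen outside the uterus. The class called clinical pregnancy with fetal heartbeat is restricted to intrauterine pregnancies. Protocol 14.4 and SAP 4.1.2 use that label for the primary efficacy variable.

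**SAP section 7** reports no major changes from the protocol.

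**The concern.** One endpoint has a narrow name in four places and a broad formula in a fifth, and the formula is the only one that the SAP offers a programmer. Followed as written, it would report a different event under the protocol's endpoint name.

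What is at stake is the interpretation of pregnancy loss by arm. Protocol 14.4 treats the efficacy variables as safety variables too, so a difference in this rate would be read as a possible harm or benefit of iDAScore. If one arm had more biochemical or ectopic pregnancies, the formula would show more non-viable pregnancies in that arm even if intrauterine loss were the same in both.

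A related conflict touches the primary variable. SAP section 1 counts an ectopic with a heartbeat as a clinical pregnancy, whereas the label used for the primary variable in protocol 14.4 and SAP 4.1.2 is the protocol 10.6 class that is intrauterine by definition.

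**Working it through.** **The plan's own figure.** The documents give no rate or count for this endpoint, so there is none to reproduce. The denominator is 520 per group (protocol 14.5; SAP section 1, sample size), which follows from 494 / 0.95 = 520.

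**The formula in terms of the protocol 10.6 classes.** Let B = biochemical, E = ectopic, V = non-viable intrauterine and C = intrauterine with heartbeat.

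- hCG positive ≈ B + E + V + C
- SAP section 1 result = hCG positive − clinical pregnancies excluding ectopics ≈ (B + E + V + C) − C = B + E + V
- Protocol 10.6 class = V

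The relation is approximate. SAP section 1 uses a heartbeat after 42 days and protocol 10.6 uses 7-9 weeks, and an ectopic with a negative test on the planned day would not enter. Taken literally (clinical minus hCG), the difference is negative; I read it as the positive difference.

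**Each hCG-positive class passed through both definitions:**

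| Class | SAP section 1 formula | Protocol 10.6 non-viable intrauterine |
|---|---|---|
| Biochemical | 1 − 0 = 1 | 0 |
| Ectopic with fetal heart | 1 − 0 = 1 | 0 |
| Ectopic by histopathology | 1 − 0 = 1 | 0 |
| Non-viable intrauterine | 1 − 0 = 1 | 1 |
| Intrauterine with heartbeat | 1 − 1 = 0 | 0 |

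The exclusion of ectopics is attached only to the subtracted term, so it keeps them in the result. If it were applied to both terms, ectopics would drop out but every biochemical pregnancy would remain.

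**Heartbeat ectopics.** Under SAP section 1 such a patient is a clinical pregnancy, hence a primary success. With a positive test she also scores 1 in the formula. Under protocol 10.6 she is neither a clinical pregnancy with fetal heartbeat nor a non-viable intrauterine pregnancy.

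**Size, non-viable endpoint.** The arm difference under the formula is (ΔB + ΔE + ΔV) / 520. With ΔV = 0, each extra biochemical or ectopic pregnancy in one arm moves it by 1/520 = 0.19 points. As a purely hypothetical case, an imbalance of 10 patients gives 10/520 = 1.92 points.

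**Size, primary endpoint.** Each heartbeat ectopic moves an arm's rate by the same 0.19 points. With both arms at the planned control rate of 35.4%, the 95% CI half-width is 1.96 × √(2 × 0.354 × 0.646 / 520) = 5.81 points, and the margin is 5 points.

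**What the planned outputs would reveal.** SAP figures 15.2-15.4 show biochemical pregnancy by arm. No listed table or figure names ectopic pregnancy, so a reader could not fully recover V from the broad count.

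**The case against.** The best defence is that the analysis route does not run through section 1. SAP 5.1.1 points to 4.1.3, whose label matches the protocol 10.6 class, and protocol 9.2 sends the reader to 10.6. On that view section 1 is loosely worded objectives text. This has force: a statistician working with both documents open could well arrive at the 10.6 class. It does not remove the point, because 4.1.3 gives no derivation and the SAP does not refer to 10.6 for one.

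A second defence is that the broader count is usable. Renaming it as all loss before a heartbeat, and declaring it, would also end the inconsistency, and it avoids the need for an ultrasound result. That is a legitimate alternative, but it would replace the protocol's named endpoint, and SAP section 7 declares no such change.

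Third, SAP section 5 puts this variable outside the fixed sequence and calls it exploratory, and section 7 denies only major changes. Both are fair and limit the severity.

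The protocol has a loose end of its own: miscarriage (9.2) and an ultrasound without a fetal heart (10.6) are not the same event.

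A reader might go further and infer that the reported rate will be inflated several-fold. The documents give no hCG-positive, biochemical or ectopic rate, so any such multiple would rest wholly on assumed figures. A reader might also infer that the sponsor deliberately redefined the endpoint. The intrauterine label kept in SAP 4.1.3 gives no support for that.

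**Conclusion.** The mismatch is real and the point is minor. The SAP section 1 formula yields biochemical plus ectopic plus non-viable intrauterine pregnancies, while SAP 4.1.3 and the protocol name only the last. This follows from the definitions and needs no assumed rate.

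The only size that the documents support is 0.19 points per misplaced patient, assuming 520 analysed per arm. The total depends on rates that are not given.

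It would be wrong to infer that the trial's main conclusion is at risk. The fixed-sequence test covers clinical pregnancy, live birth and positive hCG, so no confirmatory claim uses this variable. For the primary endpoint, the heartbeat-ectopic conflict is one of definition. At 0.19 points per case against a half-width of about 5.8 points, its effect is likely very small, although the documents do not say how many such cases to expect.

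**What to change.** - Replace the formula in SAP section 1 with the protocol 10.6 class (intrauterine pregnancy on ultrasound without a fetal heart), per randomised patient, and write that derivation into SAP 4.1.3.
- Reconcile the miscarriage wording in protocol 9.2 with that class.
- State how hCG-positive patients without an ultrasound are counted. The current formula counts them as non-viable by default.
- Report biochemical and ectopic pregnancies separately by arm.
- Reconcile SAP section 1 with protocol 10.6, protocol 14.4 and SAP 4.1.2 on ectopics with a heartbeat, using one rule for both the primary and the non-viable endpoint.
- Reconcile the 42-day and 7-9-week heartbeat timings. Otherwise a heartbeat seen early and absent later could still make a patient both a primary success and non-viable.
- Add an ITT table for the secondary efficacy analyses. SAP section 5 names ITT for them, but the table list has only FAS (14.2.2.1) and PP (14.2.2.2).
- Record the changes in SAP section 7 before unblinding.

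The cost is low: short text changes, one derived variable from a classification that protocol 10.6 already requires, and the added outputs. The downside is that the 10.6 class needs an ultrasound result. Capture must also be confirmed: protocol 14.3 lists the reason for pregnancy loss but no ectopic or non-viable intrauterine variable, and the eCRF fields are not shown.
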